 - b.) A WOCBP who agrees to follow the contraceptive guidance in Appendix D during the treatment period and for at least 30 days after the last dose of venetoclax or 18 months after the last dose of obinutuzumab, whichever is longer.
 - c.) Subjects must have a negative pregnancy test within 72 hours of beginning treatment if WOCBP.
- 9. The participant (or legally acceptable representative if applicable) provides written informed consent for the trial.
- 10. Have adequate organ function as defined in Table 1 within 28 days prior to treatment initiation.

Table 1. Adequate Organ Function Laboratory Values

Hematological	
Absolute neutrophil count	> 1500 cells per microliter unless due to bone marrow involvement
Hemoglobin	> 9 g/dL
Platelet count	> 75,000 platelets per microliter
Renal	
Creatinine clearance	> 60 mL per minute by Cockcroft-Gault equation
Hepatic	
Total bilirubin	≤ 1.5 × Upper limit of normal (ULN) OR direct bilirubin ≤ ULN for participants with total bilirubin levels > 1.5 × ULN
AST (SGOT) and ALT (SGPT)	≤2.5 × ULN, or ≤3 x ULN for patients with documented Gilbert syndrome, or ≤5 × ULN for participants with documented liver metastases

Coagulation	
International normalized ratio (INR) OR prothrombin time (PT)	≤1.5 × ULN unless participant is receiving anticoagulant therapy as long as PT or aPTT is
Activated partial thromboplastin time (aPTT)	within therapeutic range of intended use of anticoagulants

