4.2.5 Dose Modification Guidelines for Expansion Cohort

General principals/stopping rules: Dose Levels for the phase I portion of the study are as per Table 2. During the Expansion Cohort portion of the trial, dose delays/modifications are per the tables below and should be used as long as patients are deriving clinical benefit from the treatment regimen. Once the dose of an agent has been reduced, no dose re-escalation is permitted. If a scheduled dose is delayed for more than 6 weeks due to treatment-related toxicity, remove the patient from protocol therapy. No more than three dose reductions are permitted. A missed dose should not be made up, so that cycle lengths are always 28 days irrespective of the number of doses delivered in that cycle.

There will be no dose reductions for obinutuzumab. Dose reductions for CC-486 and venetoclax are per Table 4 below.

NOTE: Dose delays/dose reductions for the Dose Expansion portion of the study will be re-evaluated at the conclusion of the phase I portion of the study, and the following section is subject to revision.

Table 3A. Dose Modifications for Hematologic Toxicities. See Dose Levels for venetoclax and CC-486 in Table 4.

Observation	Action	Comments
Neutropenia ≥ gr 3	 Hold venetoclax, CC-486, and obinutuzumab (if applicable) Resume therapy at same dose level once neutropenia resolves to ≤ grade 2 If recurs, reduce by one dose level. If recurs again, reduce by one additional dose level. If recurs again, reduce by one additional dose level. 	Monitor CBC weekly. Consider use of growth factor support. If treatment is delayed by more than 6 weeks due to treatment-related toxicity, remove patient from study No more than 3 dose reductions are allowed
Thrombocytopenia ≥ gr 3	 Hold venetoclax, CC-486, and obinutuzumab (if applicable) Resume therapy at same dose level once thrombocytopenia resolves to ≤ grade 2 If recurs, reduce by one dose level. If recurs again, reduce by one additional dose level. If recurs again, reduce by one additional dose level. 	Monitor CBC weekly. No more than 3 dose reductions are allowed If treatment is delayed by more than 6 weeks due to treatment-related toxicity, remove patient from study

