5.3.4 Cycle 1 Laboratory Studies

On Days 1, 8, 15, and 22, the following studies should be obtained and reviewed prior to administration of any treatment scheduled for that day:

- Complete blood count (CBC) with differential counts including hemoglobin, hematocrit, red blood cell count, mean corpuscular volume, white blood cell count, platelet count, absolute and relative neutrophil count, absolute and relative lymphocyte count, absolute and relative monocyte count, and absolute and relative eosinophil count.
- Complete metabolic panel including serum glucose, sodium, potassium, chloride, bicarbonate, blood urea nitrogen, creatinine, total protein, albumin, alanine transaminase, aspartate transaminase, and alkaline phosphatase.
- Serum lactate dehydrogenase level.
- Serum uric acid level on Day 1 only, repeat as needed (see Appendix G)
- Serum beta-2 microglobulin level on Day 1 only.

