6.2 STATISTICAL METHODS

6.2.1 Dose Finding Cohort

A 3+3 trial design with 3 dose levels and 2 optional dose de-escalation levels will be used (see Section 4.2 for details). This rule-based design proceeds with cohorts of three patients; the first cohort is treated at a starting dose that is considered to be safe based on prior human studies, and the subsequent cohorts are treated at increasing dose levels that have been fixed in advance (Storer 1989). Safety and tolerability for the purpose of dose-finding for the three-drug combination will be assessed in the first 28-day cycle of therapy.

The definition of dose limiting toxicity (DLT) is as follows:

- Grade 3 or 4 treatment-related non-hematologic toxicity with the exceptions of fatigue, anorexia, nausea, and fever without neutropenia
- Grade 4 treatment-related hematologic toxicity (anemia, thrombocytopenia and/or neutropenia) either lasting > 7 days despite supportive care or complicated by hemorrhage
- Any grade 5 toxicity.

If none of the three patients in the first cohort experiences a DLT within a 28-day cycle, the dose level will be advanced to DL2. If one or more of the patients at a certain dose level experiences a dose-limiting toxicity, three more patients will be treated at the same dose level. If there are two or more DLTs in a cohort of 3-6 patients at dose level 1, three patients will be enrolled at DL-1. If there are two more DLTs at dose level -1, three patients will be enrolled at DL-2.

If the dose level has been advanced to level 2 already, and two or more patients in a cohort of 3-6 patients experience dose-limiting toxicity, the RP2D will be defined as dose level 1. If a dose level has been lowered to DL-1 or DL-2 and no patients experience a DLT, that dose will be the RP2D. If one patient in a cohort at DL-1 and DL-2 experiences a DLT, another three patients will be enrolled. If none of the subsequent cohort experience a DLT, the dose level will be taken as the RP2D.

If there are no DLTs at DL2, DL2 will be the RP2D.

NOTE: The RP2D will be determined based on an integrated evaluation of the efficacy, safety, and tolerability of all evaluated dosing cohorts.

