10 STUDY MONITORING, AUDITING, AND INSPECTING

10.1 STUDY MONITORING PLAN

Subject eligibility will be determined by the CRA at the central (University of Chicago) site after central pathology review of the tumor sample for eligible histology. A second review on an as-needed basis will be carried out by the study investigators.

Throughout the course of the study, monitoring of all study sites will be conducted by the site investigators and designated CRA to verify the following:

- Adherence to the protocol
- Completeness and accuracy of study data and samples collected
- Compliance with regulations
- Submission of required source documents
- Completeness and accuracy of signed informed consent forms

This protocol will undergo weekly review at the multi-institutional data and safety monitoring teleconference as per procedures specified by the UC CCC NCI-approved Data and Safety Monitoring Plan. The conference will be attended by protocol-specified investigators at the designated CRA. During the conference, the following topics will be reviewed:

- Enrollment rate relative to expectations, characteristics of participants
- Safety of study participants (Serious Adverse Event & Adverse Event reporting)
- Adherence to protocol (protocol deviations)
- Completeness, validity and integrity of study data
- Retention of study participants

Protocol deviations are to be documented using the Protocol Deviation Form and sent via email to [contact]. Deviations that are considered major because they impact subject safety or alter the risk/benefit ratio, compromise the integrity of the study data, and/or affect subjects' willingness to participate in the study must be reported within 7 days. The University of Chicago CRA ([contact]) should be contacted with any questions about how to report deviations. All major protocol deviations should also be reported to the local IRB of record according to their policies and procedures.

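### Table 1 waives the neutrophil limit for marrow involvement with no floor, so a dose-finding patient with baseline grade 3-4 neutropenia may start all three drugs at the assigned dose level

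*Combined protocol and SAP*

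**What the plan says.** Section 3.3, Table 1, requires a neutrophil count of "> 1500 cells per microliter unless due to bone marrow involvement". The other exceptions in the table carry a bound. Transaminases, for instance, may go to "≤5 × ULN for participants with documented liver metastases", raised total bilirubin is accepted only if direct bilirubin is within normal limits, and clotting times on anticoagulants must be in the therapeutic range. Hemoglobin has no exception, and neither does the platelet limit, "> 75,000 platelets per microliter".

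For the first cycle, Section 5.3.4 states: "On Days 1, 8, 15, and 22, the following studies should be obtained and reviewed prior to administration of any treatment". It names no value at which treatment may not start.

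Table 3A in Section 4.2.5 holds all drugs for neutropenia of grade 3 or higher and resumes at grade 2 or lower. The section introduces its tables with: "During the Expansion Cohort portion of the trial, dose delays/modifications are per the tables below". For phase I it points only to the dose levels in Table 2.

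Section 6.2.1 defines the hematologic DLT as "Grade 4 treatment-related hematologic toxicity (anemia, thrombocytopenia and/or neutropenia) either lasting > 7 days despite supportive care or complicated by hemorrhage". It has no rule for a cytopenia present at baseline. The same section adds: "The RP2D will be determined based on an integrated evaluation of the efficacy, safety, and tolerability of all evaluated dosing cohorts".

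**The concern.** Dose-finding patients receive all three drugs from Cycle 1 (Section 1.1.7). At dose levels 1 to 3 that means obinutuzumab 1000 mg on days 1, 8 and 15, CC-486 200 mg and venetoclax 400 to 800 mg (Table 2). Section 7.4.3 reports severe neutropenia with each drug, and Section 1.1.6.3 gives overlapping neutropenia as a main reason for capping CC-486. A patient with little neutrophil reserve can nevertheless begin the combination, at a grade for which the protocol's own expansion rule would withhold it.

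The second consequence concerns reading the DLT. For an entrant already at grade 4, disease alone can satisfy both the grade and the duration of more than 7 days, leaving treatment-relatedness as the only discriminating element. At a level of three to six patients, one such call can decide whether the level passes.

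**Working it through.** **Is there a floor elsewhere?** The plan states no figure on this point, so the first check is textual.

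- Section 3.4: no exclusion mentions neutrophils.
- Section 5.3.4: the Day 1 count is reviewed, with no threshold.
- Section 4.2.5, Table 3A: a mandatory hold, but written for expansion.
- Section 4.2.4: delays obinutuzumab for neutropenia potentially attributable to it. The heading says expansion, and a count that was low before the first dose is not attributable to the drug.
- Section 7.4.3: applies to both cohorts, but delay, dose reduction and growth factor are only to be considered.
- Section 7.4.4.1: prophylaxis is left to clinical judgment.

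None sets a minimum count for starting.

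**How much could it move a dose decision?** All rates below are assumptions; the documents give none. A level is taken to pass with no DLT in three patients, or one in three followed by none in three:

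Pass(p) = (1−p)³ + 3p(1−p)²·(1−p)³

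- Pass(0.15) = 0.614 + 0.200 = 0.814
- Pass(0.33) = 0.301 + 0.134 = 0.434

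Let q be the share of entrants at grade 4, m the chance that such a patient is wrongly scored as a DLT, and s the share of DLTs that are neutropenia.

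*Average effect, wrongly scored.* The rate becomes 1 − (1−0.15)(1−qm); the reference is 0.814.

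| q | m = 25% | m = 50% | m = 100% |
|---|---|---|---|
| 1% | 0.810 | 0.805 | 0.797 |
| 2% | 0.805 | 0.797 | 0.779 |
| 5% | 0.792 | 0.770 | 0.725 |

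*Average effect, true DLT discounted.* The rate becomes 0.33(1−qs); the reference is 0.434.

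| q | s = 25% | s = 50% | s = 100% |
|---|---|---|---|
| 1% | 0.436 | 0.438 | 0.441 |
| 2% | 0.438 | 0.441 | 0.447 |
| 5% | 0.442 | 0.451 | 0.467 |

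*Given one such patient among the first three at a level.*

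- Wrongly scored, p = 0.15: (1−m)·Pass(p) + m(1−p)⁵, with 0.85⁵ = 0.444. This gives 0.721, 0.629 and 0.444 at m = 25%, 50% and 100%.
- Discounted, p = 0.33, r = p(1−s): (1−r)(1−p)² + [r(1−p)² + (1−r)·2p(1−p)]·(1−p)³. At s = 100%, r = 0 and the result is 0.449 + 0.442 × 0.301 = 0.582. At s = 25% and 50% it is 0.471 and 0.508.
- Chance of having such a patient among the first three: 1 − (1−q)³ = 3.0%, 5.9% and 14.3% at q = 1%, 2% and 5%.

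**What would a floor do?** The documents cite CTCAE version 5 without listing its limits, so take grade 4 as below 500 and grade 3 as below 1000. An entrant already at grade 4 needs no fall to meet the grade part of the DLT. From a starting count A, the fall must exceed 1 − 500/A: 33% from 750, 50% from 1000, 60% from 1250 and 67% from the standard limit of 1500.

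**The case against.** The strongest reply is that existing text already covers most of this. Section 8.2.1 bases adverse events on changes, Section 8.1 supplies a five-level attribution scale, and the DLT must be treatment-related. Unchanged neutropenia from disease should therefore not be scored, and the m = 100% column assumes investigators ignore those rules. A reader might infer that baseline grade 4 neutropenia counts automatically as a DLT; the documents do not support that.

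The cohort scope of Section 4.2 is also less clear than its headings. Section 4.2.2 mentions re-escalation in the dose-finding cohort, Section 4.2.4 gives an instruction for dose-finding patients, and Section 7.4.3 refers to Section 4.2 without naming a cohort. A dose-finding investigator might well apply the obinutuzumab delay on Days 8 and 15. Further safeguards exist: active infection is excluded, patients with grade 3 or 4 neutropenia should be monitored frequently, infection monitoring is mandatory at every visit (Section 7.4.4), safety is reviewed weekly (Section 10.1), and "Subject eligibility will be determined by the CRA at the central (University of Chicago) site". Section 7.4.4 also says that neutropenia is not an independent infection risk factor with venetoclax.

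All of this stands as mitigation, and it makes the m = 100% and s = 100% results worst cases. It does not close the gap. None of it sets a count below which the first dose is withheld, and central eligibility review has no minimum to apply. The waiver is a deliberate sponsor choice; the missing part is its lower bound.

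**Conclusion.** The gap is real and worth a small change. Its main weight is patient safety in the dose-finding cohort. The statistical effect is secondary: averaged over patients, the pass probability moves from 0.814 to between 0.810 and 0.725, or from 0.434 to between 0.436 and 0.467, before the integrated RP2D evaluation is applied. The larger shifts, to 0.444 or 0.582, need such a patient among a level's first three together with the extreme scoring assumption. Everything numerical rests on assumed values of q, m, s and the true DLT rates, and on assumed grade limits. Such patients are probably rare, because hemoglobin above 9 g/dL and the platelet limit must still be met.

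Three stronger readings are tempting and are not supported. One is that the RP2D would be unreliable: the average effect is too small, and the final choice is not mechanical. Another is that every patient admitted this way gets a maximal regimen: treatment is at the assigned level, and venetoclax at dose level 1 is half that at level 3. The third is that the expansion cohort has the same problem: there, Table 3A read literally would hold treatment, so the issue is a conflict between eligibility and the hold rule. No stated alpha, power or sample size is affected.

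**What to change.** For the dose-finding cohort, keep the marrow waiver but add a minimum neutrophil count, confirmed on the Cycle 1 Day 1 blood count. It should be no worse than grade 2, for example at least 1000 per microliter, which matches Table 3A's own condition for resuming under the grade limits assumed here. The sponsor should confirm the value. The protocol also uses 1000 in Section 8.2.7 to define late-onset and prolonged neutropenia, though not for eligibility. The alternative is to drop the waiver in dose finding only.

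For expansion, state how the waiver and Table 3A fit together when the dose-modification plan is reviewed, as Sections 4.2.5 and 6.2.2 already foresee.

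The cost is a line in Table 1 and a check on a sample already scheduled, with no new procedure and no change in planned numbers. A few patients with marrow-related counts below the floor become ineligible for dose finding; the documents do not say how many. Entrants between the floor and 1500 remain partly confounded, so the floor reduces the DLT ambiguity without removing it.

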3.4 EXCLUSION CRITERIA

Participants are excluded from the study if any of the following criteria apply:

- 1. A WOCBP who has a positive urine pregnancy test within 72 hours prior to treatment allocation (see Appendix D). If the urine test is positive or cannot be confirmed as negative, a serum pregnancy test will be required. Note: in the event that 72 hours have elapsed between the screening pregnancy test and the first dose of study treatment, another pregnancy test (urine or serum) must be performed and must be negative in order for the subject to start receiving study medication. Women who are known to be pregnant or who are breastfeeding are excluded from the study (lactating women must agree not to breastfeed for the duration of the trial).
- 2. Has received any prior systemic therapy other than anti-CD20 monoclonal antibody or radiotherapy prior to the first dose of study medication. Subjects must not have had a prior dose of anti-CD20 monoclonal antibody therapy within 28 days prior to the first dose of study medication.
- 3. Known hypersensitivity or allergy to any of the study drugs, xanthine oxidase inhibitors and/or rasburicase, mannitol, murine products, or any components of the drug formulations.
- 4. History of severe allergic or anaphylactic reaction to humanized or murine monoclonal antibodies.
- 5. History of other malignancy that could affect compliance with the protocol or interpretation of results.
 - a.) Patients with a history of curatively treated basal or squamous cell carcinoma or stage 1 melanoma of the skin or in situ carcinoma of the cervix are eligible.
 - b.) Patients with a malignancy that has been treated with surgery alone with curative intent will also be excluded. Individuals in documented remission without treatment for 2 years prior to enrollment may be included at the discretion of the sponsor-investigator.
- 6. Has histologic or clinical evidence of transformation to an aggressive lymphoma subtype including grade 3b FL.
- 7. Received the following agents within 7 days prior to the first dose of venetoclax:
 - a.) Steroid therapy for anti-neoplastic intent
 - b.) A strong or moderate CYP3A inhibitor (see Appendix H)
 - c.) CYP3A inducers (see Appendix H)

- d.) Consumed grapefruit, grapefruit products, Seville oranges (including marmalade containing Seville oranges), or star fruit within 3 days prior to the first dose of venetoclax.
- e.) P-gp inhibitors or narrow therapeutic index P-gp substrates
- 8. Evidence of significant, uncontrolled concomitant diseases that could affect compliance with the protocol or interpretation of results or that could increase risk to the patient, including renal disease that would preclude chemotherapy administration or pulmonary disease (including obstructive pulmonary disease and history of bronchospasm).
- 9. Known active bacterial, viral, fungal, mycobacterial, parasitic, or other infection (excluding fungal infections of nail beds) at study enrollment, or any major episode of infection requiring treatment with IV antibiotics or hospitalization (relating to the completion of the course of antibiotics) within 4 weeks prior to Cycle 1, Day 1. Uncontrolled systemic fungal, bacterial or viral infection (defined as ongoing signs/symptoms related to the infection without improvement despite appropriate antibiotics, antiviral therapy and/or other treatment) will result in study exclusion. Caution should be exercised when considering the use of any of the study medication in patients with a history of recurring or chronic infections.
- 10. Clinically significant history of liver disease, including viral or other hepatitis, current alcohol abuse, or cirrhosis.
- 11. Presence of positive test results for hepatitis B virus (HBV), hepatitis B surface antigen (HBsAg), or hepatitis C (HCV) antibody. Patients who are positive for HCV antibody must be negative for HCV by polymerase chain reaction (PCR) to be eligible for study participation. Patients with occult or prior HBV infection (defined as positive total hepatitis B core antibody [HBcAb] and negative HBsAg) may be included if HBV DNA is undetectable. These patients must be willing to undergo monthly HBV DNA testing.
- 12. Receipt of live-virus vaccines within 30 days prior to the initiation of study treatment
- 13. Malabsorption syndrome, inability to swallow a large number of pills, or other condition that precludes enteral route of administration.
- 14. A history of progressive multifocal leukoencephalopathy (PML) or known prior infection with the John Cunningham (JC) virus.
- 15. Significant active cardiac disease within the previous 6 months including New York Heart Association class 4 heart failure, unstable angina, or myocardial infarction.

3.5 VULNERABLE SUBJECTS

No children, pregnant women, fetuses, or prisoners will be included in this study. Persons with cognitive impairment who are found to have capacity for medical decision making and who can provide their own informed consent will be allowed to participate in the study. Economically disadvantaged persons will not be specifically targeted or excluded from the study. Patients will be

recruited from the diverse general population of FL patients requiring treatment at University of Chicago Medicine and other study sites to allow for generalizable results to routine community practice.

3.6 Subject Identification & Recruitment

Patients will be identified by primary oncologists and study investigators in the ordinary course of care for FL patients. The trial will be publicized to community physicians through fliers and lectures, and will be publicized with regional academic centers through academic gatherings and meetings.

3.7 LOCATION

Patients will be seen for each study visit in the Duchossois Center for Advanced Medicine at the University of Chicago Hyde Park Campus, or the equivalent primary oncology clinic at each participating site. Infusional therapy will be administered in the outpatient intravenous therapy center of each participating site.

